	Nutrient Profiling Model score of the products the participants select in
	the shopping task. Secondary outcomes include selection outcomes (e.g.,
	Guiding Stars scores of selections, calorie density of selections) and
	psychological outcomes (e.g., noticing of trial labels,
Statistical and	We will use ordinary least squares regression to examine the effect of the
Analytic Plan	front-of-package labeling systems on continuous outcomes (e.g.,
	healthfulness, calorie density). We will use Poisson regression to examine
	the effect of the front-of-package labeling system on count outcomes (i.e.,
	number of products selected that were high in 1 or more nutrient of
	concern). We will use logistic regression to examine the effect of the
	front-of-package labeling systems on binary outcomes (e.g., noticing of
	the front-of-package labels). Finally, we will use mixed effects logistic
	regression to examine the effect of the front-of-package labeling systems
	on consumer understanding.
Data and Safety	• The principal investigators are responsible for data quality
Monitoring Plan	management and ongoing assessment of safety.

Introduction

The goal of the analyses described here is to use data we collected through an online randomized experiment to examine consumer responses to different front-of-package food labeling systems. These analyses examine the effects of six front-of-package food labeling systems: 1) positive labels, 2) spectrum labels, 3) FDA high in labels, 4) FDA traffic light labels, 5) FDA high in labels plus positive labels, or 6) FDA traffic light labels plus positive labels.

This analysis plan pre-specifies the analyses before collecting data and therefore serves as our ex-ante planned analysis.

Study Protocol

Participants will complete an online randomized experiment. After providing informed consent, participants will be directed to complete a shopping task in a naturalistic online store. Participants will be instructed to shop as they usually would for items in the following categories: non-alcoholic beverages (e.g., juice, coffee, tea, soda, sports drinks, water), breads and baked goods, breakfast cereals, soups, boxed and frozen meals, and snacks (e.g., chips, crackers, nuts, applesauce, dried fruit). They will be given a budget based on average spending in these categories in a large supermarket chain. To complete the shopping task, participants will be required to spend between 0.5 and 1.5 times the budget, but otherwise will be free to select whichever products they choose. To incentivize truthful responding, participants will be instructed that 1 in 50 will be chosen at random to receive their selections delivered to their home and the remainder of their shopping budget as an electronic gift card.

After completing the shopping task, participants will respond to an online survey programmed in Qualtrics.

Statistical Considerations

General Principles

We will use a two-sided critical alpha of 0.05 to conduct all statistical tests. All confidence intervals presented will be 95% and two-sided. Because we expect minimal missing data based on prior similar studies,^{1–3} we will use complete case analysis to handle any missing data in analyses of the primary and secondary outcomes.

Primary Outcome

The primary outcome is healthfulness of participants' selections, operationalized as the weighted average Ofcom Nutrient Profiling Model score of the products the participants select in a shopping task, weighted by the number of servings in each product.

Secondary Outcomes

The secondary outcomes are:

- Selection outcomes:
 - 1. Guiding Stars score
 - 2. Number of items selected that are high in ≥ 1 nutrient of concern
 - 3. Calorie density, kcal per 100g
 - 4. Sugar density, g per 100g
 - 5. Sodium density, mg per 100g
 - 6. Saturated fat density, g per 100g
 - 7. Fiber density, g per 100g
 - 8. Protein density, g per 100g
 - 9. Total calories selected, kcal
 - 10. Total sugar selected, g
 - 11. Total sodium selected, mg
 - 12. Total saturated fat selected, g
 - 13. Total fiber selected, g
 - 14. Total protein selected, g
 - 15. Total items selected
 - 16. Spending, USD (\$)
- Psychological outcomes
 - 17. Consumer understanding, % correctly identifying healthier item
 - 18. Noticing, % who noticed the labels
 - 19. Use of labels, % who used the labels when shopping
 - 20. Thinking about health
 - 21. Negative emotional reactions
 - 22. Perceived helpfulness
 - 23. Perceived understandability
 - 24. Perceived trustworthiness
 - 25. Public support for requiring this labeling system

Statistical Methods

- 1. We will describe participant characteristics by trial arm. We will use means and standard deviations to characterize continuous variables (such as age), and frequencies and percentages to characterize categorical variables (such as gender and educational attainment).
- 2. Analyses of the primary outcome:
 - a. We will use ordinary least squares regression to evaluate the effects of the frontof-package labeling systems on healthfulness of participants' selections. We will regress healthfulness on indicator variables for each of the front-of-package labeling systems, excluding the positive labeling system as the referent category. We will use the models to estimate average differential effects (ADEs, i.e., differences in predicted means between groups) for each labeling system compared to the positive labeling system.
 - b. We will test whether the effects of the 5 labeling systems (other than the positive labeling system) on healthfulness of participants' selections differ from one another using Wald tests.
 - c. We will test whether the effects of the labeling systems on healthfulness of participants' selections are moderated by nutrition literacy (assessed with an adapted version of the Newest Vital Sign measure of health literacy⁴), annual household income, and educational attainment. To test for moderation, we will regress healthfulness on the moderator, indicators for each of the front-of-package labeling systems, and the interaction between the labeling systems and the moderator, using separate models for each moderator. We will test the joint significance of the interaction terms and report effects of the labeling systems at different levels of the moderator.
- 3. Analyses of secondary outcomes:
 - a. We will use ordinary least squares regression to evaluate the effects of the frontof-package labeling systems on continuous secondary outcomes (e.g., Guiding Stars score, calorie density); logistic regression to evaluate effects on binary outcomes (e.g., noticing); Poisson regression to evaluate effects on count outcomes (e.g., number of items selected that are high in ≥1 nutrient of concern); and mixed effects logistic regression to evaluate effects on repeated measures binary outcomes (i.e., consumer understanding of product healthfulness). We will regress the outcome on indicator variables for each of the front-of-package labeling systems, excluding the positive labeling system as the referent category. We will use the models to estimate ADEs for each labeling system compared to the positive labeling system.

Sample Size Needs

We plan to collect data from 5,610 participants. We used G*Power to estimate sample size needs.⁵ We estimated sample size needs to detect an effect of each labeling system vs. the positive labeling system. Assuming an alpha=0.05, a sample of 5,610 will yield 90% power to detect a standardized effect of Cohen's d=.15 or larger and 80% power to detect a standardized

effect of d=.13 or larger of each labeling system vs. the positive labeling system. These effects would be considered small.⁶ Prior studies comparing different front-of-package labeling systems to positive front-of-package labeling found similar effect sizes.^{1,3,7}

Exclusions and Outliers

We will exclude participants who do not complete the shopping task (for whom we will not have data on the primary outcome) or who complete the survey implausibly quickly (defined as completing in less than one-third of the median completion time).

References

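### Poisson regression is specified for the count of high-in items with no allowance for variance different from the mean, so with ordinary standard errors the promised 5% tests and 95% intervals are not assured

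*SAP*

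**What the plan says.** Item 3a of Statistical Methods assigns "Poisson regression to evaluate effects on count outcomes", giving the count of high-in items (secondary outcome 2) as the example. The model contains arm indicators only, with positive labels as the reference. From it, "We will use the models to estimate ADEs for each labeling system compared to the positive labeling system". The Protocol Synopsis also specifies Poisson regression, for "the effect of the front-of-package labeling system on count outcomes (i.e".), and there lists outcome 2 alone.

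General Principles sets the error rates for every analysis: "We will use a two-sided critical alpha of 0.05 to conduct all statistical tests" and "All confidence intervals presented will be 95% and two-sided".

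On how the counts arise, the Study Protocol section says "participants will be required to spend between 0.5 and 1.5 times the budget", but they "otherwise will be free to select whichever products they choose".

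Nowhere does the SAP say how standard errors for the Poisson model are computed. It mentions no overdispersion or underdispersion, sandwich variance, quasi-Poisson scale or negative binomial alternative, and it gives no mean or variance for the counts.

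**The concern.** Ordinary Poisson standard errors are derived from the fitted mean alone, because the model takes the variance to equal it. If the real variance is larger, the standard errors are too small: label effects on high-in items would be declared too often and intervals would be too narrow. If the real variance is smaller, the tests are conservative and power is lost. Both consequences apply only if model-based errors are used.

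The counts here depend on how much each household spends within a threefold range, what it buys and how far it favours high-in products. There is no reason to expect these to combine into a variance equal to the mean. Outcome 2 bears directly on the arms with high-in labels, and it yields five contrasts with the positive label.

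**Working it through.** **Inputs from the SAP.** Two-sided alpha 0.05 and 95% intervals (General Principles); 5,610 participants (Sample Size Needs); six arms (Introduction); spending between 0.5 and 1.5 times the budget (Study Protocol). Equal allocation, 5,610/6 = 935 per arm, is an assumption.

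**The plan's own figure.** The SAP's power statement concerns a standardized mean difference, not the counts, and it reproduces. With n = 935 per arm, power = Φ(d·√(n/2) − 1.96).
- d = 0.15: Φ(3.243 − 1.96) = 90.0%.
- d = 0.13: Φ(2.811 − 1.96) = 80.3%.

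The sample size is not in question. There is no corresponding figure for the count outcome.

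**Step 1: type I error under model-based errors.** Let v = variance/mean, the same in both arms. The true standard error is √v times the model-based one, so

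type I error = 2·[1 − Φ(1.96/√v)], and coverage = 1 − type I error.

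| v (assumed) | Type I error | Coverage |
|---|---|---|
| 0.75 | 2.4% | 97.6% |
| 1 | 5.0% | 95.0% |
| 1.25 | 8.0% | 92.0% |
| 1.5 | 11.0% | 89.0% |
| 2 | 16.6% | 83.4% |

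The error passes 7.5% at v = 1.21 and 10% at v = 1.42.

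Simulation agrees (two arms of 935, mean 5 or 10, 10,000 replicates). Model-based tests rejected in 5.0% to 5.2% for Poisson counts, 11.3% at v = 1.5 and 16.4% to 17.0% at v = 2. Robust tests rejected in 4.6% to 5.2% in every setting run.

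**Step 2: which v is plausible if only spending varies?** Assume the number of items N is proportional to spending, with mean m = 10, 20 or 30. Assume spending is uniform (CV² = 1/12) or triangular (CV² = 1/24) on 0.5 to 1.5 times the budget, and that each item is high-in with probability 0.5. Then v = 0.5 + 0.5·m·CV².

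| Spending | m | v | Type I error |
|---|---|---|---|
| Uniform | 10 | 0.92 | 4.1% |
| Uniform | 20 | 1.33 | 9.0% |
| Uniform | 30 | 1.75 | 13.8% |
| Triangular | 10 | 0.71 | 2.0% |
| Triangular | 20 | 0.92 | 4.1% |
| Triangular | 30 | 1.12 | 6.5% |

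Three settings are conservative and three are liberal. At the lowest, v = 0.71, a contrast with 80% power under correct errors has Φ(2.802 − 1.96/√0.708) = 68%.

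**Step 3: let the high-in share also vary between people.** Give the share a mean of 0.5 and a standard deviation s, independent of N. Then

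v = {(0.25 − s²) + m·[(1 + CV²)(0.25 + s²) − 0.25]}/0.5.

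- s = 0.10: v runs from 0.90 to 2.38 and the type I error from 3.8% to 20%; five of the six settings exceed 5%.
- s = 0.20: v runs from 1.46 to 4.27 and the error from 10.5% to 34%; all six exceed 10%.

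Check at m = 20, triangular spending, s = 0.20: the formula gives v = 2.50 and 21.5%. Simulation (935 per arm, 4,000 replicates) gave 21.8% model-based and 5.2% robust.

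**Step 4: point estimates.** With arm indicators only, the fitted Poisson means are the arm means, so the ADEs do not depend on the variance option. In one simulated six-arm data set (935 per arm, mean 8, variance 16) an ADE was 0.153 under both Poisson and OLS. Its standard error was 0.130 model-based and 0.185 sandwich. Theory gives √(2·8/935) = 0.131 and √(2·16/935) = 0.185.

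**The case against.** The strongest objection is that the SAP names a model and not a standard-error method. Poisson regression is compatible with sandwich errors, and an analyst could use them without departing from the text. This stands to the extent that every figure above is conditional on model-based errors. It does not remove the point. Unqualified Poisson regression is naturally run with the model's own errors, and the option changes the intervals and tests of a pre-specified outcome.

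Second, the SAP gives no dispersion figure, so neither size nor direction can be read from it. This stands. A reader might infer that false positives are certain, or that rates of 17% or more are to be expected. The documents support neither. With spending variation alone, half of the assumed settings are conservative and the largest error is about 14%. Higher rates need further assumptions about how people differ.

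Third, to say that validity requires variance equal to the mean in each arm is too strong. With equal means and arm sizes, variance-to-mean ratios of 0.5 and 1.5 in the two arms average (0.5 + 1.5)/2 = 1, and the contrast keeps its 5% size. The strict condition is that the two arms' combined variance equals the Poisson value.

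Fourth, a reader might extend the point to secondary outcome 15, "Total items selected". The SAP does not assign it to Poisson regression. The synopsis lists outcome 2 as the count outcome, while 3a offers it as an example. That leaves a classification unstated but is no contradiction, and if outcome 15 goes to OLS the problem does not arise.

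**Conclusion.** The point holds in a limited form. Followed as written with ordinary Poisson errors, the stated method does not assure the SAP's own 5% and 95% for secondary outcome 2. Under the assumed range with spending variation only (v about 0.7 to 1.75), the type I error is about 2% to 14%. It is higher if the high-in share also varies between people, although underdispersion remains possible. These figures rest on assumed item numbers, spending distributions and shares, a common v in the two arms, and model-based errors.

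The firm reach is one of 25 secondary outcomes. A reader should not infer that the trial's main conclusion is at risk: the primary OLS analysis, the sample size and every arm mean and ADE are untouched. The change should be made because it is almost free, not because the damage is known to be large.

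**What to change.** In Statistical Methods, item 3a, write: *Poisson regression with heteroskedasticity-robust (sandwich) standard errors for all ADEs and tests on count outcomes*. Use the same wording in the synopsis. A quasi-Poisson dispersion parameter would also serve; the sandwich form is preferred because it assumes no form for the variance.

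As an optional tidy-up, state whether outcome 15 is a count outcome. Under sandwich errors the choice hardly matters, since Poisson and OLS on arm indicators give identical ADEs and near-identical standard errors.

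The cost is one phrase and one software option. If the counts are truly Poisson, the robust test had a simulated size of about 5.1% at 935 per arm, so almost nothing is given up.
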